# 2.11 Other Exploratory analyses

NA

# 2.12 Interim analysis

There are no interim analyses during the study.

# 3 Sample size calculation

In previous studies using the same techniques (i.e. C-acetate PET scan and echocardiography), beta-blockers in drug-naïve subjects increased cardiac efficiency by 45% (Beanlands 2000). In later studies using e.g. new biventricular pacing techniques in previously medicated subjects, the cardiac efficiency was improved by 20% (Sundell 2004). Therefore, we assume that the clinically significant change in cardiac efficiency in medicated subjects would be about 20%. In our previous studies in subjects with heart failure (Nesterov 2015, Tuunanen 2008), the same subjects were studied twice in the interval of 3 months, the coefficient of variation (CV%) of Kmono in placebo group was 18.4% and in efficiency 19.7%. Based on sample size calculations, in order to detect a 15% change in cardiac efficiency, 27 subjects would need to be included in each treatment arm (assuming  $\alpha = 0.05$  and  $\beta = 0.2$ ). Due to potential drop outs during the study, the target is to enroll 30 + 30 subjects in the treatment arms.

# 4 Change to protocol specified analyses

An additional parameter, viable myocardium energetic efficiency, is added as a sensitivity analysis for the primary endpoint as described in section 2.4.5.

In the protocol it was stated that all summary statistics will be done by dose level. Split of summary statistics by dose level, ie stratification factor, will be limited to the subject disposition, primary endpoint and overview of TEAEs.

# 5 Appendix

# 5.1 Imputation rules

If the visit 3 assessment for the primary endpoint is missing for a subject then this will be imputed using a monotone regression approach including treatment and stratification as class variables. One hundred imputations will be done. Each replication of the data, including the imputed missing values, will then be analyzed using the ANCOVA used in the primary analysis, and estimates will be pooled using proc MIANALYZE SAS®.

# 5.1.1 Study drug

Actual dates and time points of study drug adminstrations are not captured in the eCRF. The last drug date is recorded on the study termination page, the first drug date is assumed to be on the day of randomization.

# 5.1.2 AE date imputation

AEs with incomplete dates will be regarded as TEAEs if year and month are available and are the same as the date of first dose of randomized treatment or if only year is available and is the same year as the date of first dose of randomized treatment.

| Novartis | Confidential | Page 22 of 30          |
|----------|--------------|------------------------|
| SAP      |              | Study No. CLCZ696BFI03 |

## 5.1.3 Concomitant medication date imputation

For medication and therapies with partial dates:

- If start date is completely missing, it will be assumed that the medication started before date of first administration of randomized treatment.
- If end date is completely missing and ongoing is not ticked, it will be assumed that the medication ended before date of first administration of randomized treatmenttreatment.
- For medications/therapies where only partial dates are available, either only year or year and month, then this information will be used in analogy with how complete dates are used for classification.

Relative day will not be calculated for medications with incomplete dates.

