# 6.5.1 Prohibited treatments during the study

Concomitant medication(s) that could affect the outcome of the study, interfere with the evaluation of the results or constitute a health risk for the study subject, as judged by

the investigator. These include e.g. vasoactive supporting medication(s) that have known effects on cardiac efficiency.

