# 2.2 Analysis sets

The following analysis sets will be used for the statistical analysis and presentation of data:

- The safety analysis set (SAF) will consist of all randomised subjects who received at least one dose of the study medication in the treatment period, provided that there was at least one safety follow-up performed for the subject.
- The full analysis set (FAS) will consist of all randomised subjects who have received at least one dose of study medication in the treatment period and have at least one post-baseline assessment of any efficacy endpoints.
- The per protocol set (PPS) will consist of all subjects in the FAS who received at least 75% of the study drug doses, and do not have any other major protocol violations which will affect the assessment of efficacy. Major/important protocol violations may include, but are not limited to, the following:
  - Non-fulfillment of all inclusion criteria
  - o Fulfillment of at least one exclusion criteria
  - Use of certain concomitant medications (this will be judged on a case to case basis, depending on extent of treatment)

The final criteria for PPS, regarding which protocol deviations that warrant exclusions, will be determined when all data on protocol violations/deviations are available and before breaking the blind. The decision of what protocol violations/deviations will lead to exclusion as well as the final classification of subjects according to analysis sets will be documented and signed off before breaking the blind. These decisions will be documented in a separate Pre-Analysis Review document.

The FAS is considered as the primary analysis dataset, and will be used for all primary and secondary efficacy analyses. The primary efficacy analysis will be repeated using the PPS.

| Novartis | Confidential | Page 13 of 30          |
|----------|--------------|------------------------|
| SAP      |              | Study No. CLCZ696BFI03 |

Any significant discrepancy between the results from the FAS and the PPS will be analysed and discussed.

Baseline presentations will be based on the safety set.

Safety presentations will be based on the safety set.

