## 2.3.4 Prior, concomitant and post therapies

All concomitant treatments administered during the study must be recorded on the CRF page for concomitant treatments. No other investigational treatment is allowed to be used during the study. A study subject must not participate concurrently or have participated in any other clinical drug study within 3 months prior to the first study treatment administration of this study.

All concomitant medications/therapies will be classified according to ATC level 3 group text and World Health Organization (WHO) Drug Dictionary preferred name. The medications will be classified into categories Prior, Concomitant and Post IMP based on start date and end date in relation to IMP exposure (randomized double-blinded treatment).

- Prior medications are those were end dates of the medication/therapy are strictly before date of first administration of IMP.
- Concomitant medications are those for which the period between their start dates and end dates coincide with exposure to study drug and can be further classified into:
  - Concomitant medications starting prior to first exposure of IMP having start dates strictly before first exposure of IMP and end dates on same date or after date of first administration of IMP or are ongoing.
  - Concomitant medications starting on the date of first administration of IMP or after but before or on the date of last administration of IMP
- Post medications are those for which the start dates are strictly after date of last administration of IMP

The concomitant medications will be presented in a summary table broken down on timing in relation to IMP (i.e., Prior, Concomitant and Post). Each subject will only be counted once for each medication and timing category, on a preferred name level in each period.

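### The SAP's rule for a wholly missing medication end date, with ongoing not ticked, ignores the start date, so it can label on-treatment use as Prior and can create end dates that precede the start

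*SAP*

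**What the plan says.** SAP 5.1.3 gives three rules for medication dates.

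- No start date: "If start date is completely missing, it will be assumed that the medication started before date of first administration of randomized treatment".
- No end date and the ongoing box not ticked: "If end date is completely missing and ongoing is not ticked, it will be assumed that the medication ended before date of first administration" of randomised treatment.
- Only a year, or a year and month: "this information will be used in analogy with how complete dates are used for classification".

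SAP 5.1.3.1, on other imputations, is marked not applicable.

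SAP 2.3.4 then sorts each medication by timing. Prior depends on the end date alone: "Prior medications are those were end dates of the medication/therapy are strictly before date of first administration of IMP". The general Concomitant definition needs overlap with treatment: "Concomitant medications are those for which the period between their start dates and end dates coincide with exposure to study drug". Its second sub-category is worded on the start date alone: "Concomitant medications starting on the date of first administration of IMP or after but before or on the date of last administration of IMP". Post is also defined by the start date alone, as a start after the last dose. The three categories are the columns of a summary table. Medications are also listed individually (SAP 5.6, listing 16.2.11).

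SAP 2.2 names, among possible major violations for the per protocol set (PPS), "Use of certain concomitant medications (this will be judged on a case to case basis, depending on extent of treatment"). Protocol 6.5.1 gives as examples of prohibited treatment "vasoactive supporting medication(s) that have known effects on cardiac efficiency".

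**The concern.** A record with no end date and no ongoing tick leaves it unknown whether the drug was taken during randomised treatment. The rule settles every such case as not taken. Where the recorded start falls on or after the first dose, that answer contradicts the data, because the drug would have stopped before it began.

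At stake is whether the medication table describes on-treatment exposure correctly. Some concomitant drugs can themselves alter cardiac efficiency, the primary endpoint, so a reader will use this table to see whether background treatment differed between arms after randomisation. A rule that moves uncertain records out of the on-treatment column makes exposure look smaller than it may have been. There is also a practical problem: a programmer cannot apply 5.1.3 and 2.3.4 together without making a choice that the SAP does not record.

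**Working it through.** The documents give no figure to reproduce, because this is a check of rules and not of arithmetic. The rules in SAP 5.1.3 were applied to example records, and the results were classified under SAP 2.3.4.

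**Inputs**
- First dose: day 1, the day of randomisation (SAP 5.1.1).
- Last dose: day 56. This is an assumption, from a treatment period of about 8 weeks (8 × 7 = 56). In the trial it would be the date on the study termination page.
- Start days of -30, 20 and 60 are illustrative. They stand for a start before, during and after treatment.

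**Tests applied to each record after imputation**
- Prior: end < day 1.
- Concomitant, first sub-category: start < day 1, and end ≥ day 1 or ongoing.
- Concomitant, second sub-category: day 1 ≤ start ≤ day 56.
- Post: start > day 56.
- Overlap with treatment (the general Concomitant definition): start ≤ end, start ≤ day 56 and end ≥ day 1.

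**Results**

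| Record | End used | Categories met | Overlap with treatment? |
|---|---|---|---|
| Start day -30, no end, not ongoing | before day 1 | Prior only | No |
| Both dates missing, not ongoing | before day 1 | Prior only | No |
| Start day 20, no end, not ongoing | before day 1, so end < start | Prior and Concomitant (second sub-category) | No |
| Start day 60, no end, not ongoing | before day 1, so end < start | Prior and Post | No |
| Start day -30, ongoing ticked | open | Concomitant only | Yes |
| Start day 20, ongoing ticked | open | Concomitant only | Yes |
| Start day 20, end day 30 | day 30 | Concomitant only | Yes |

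The first two rows are classified without conflict, but they rest on an assumption that may be false. The third and fourth rows have impossible dates and two categories each. The third also fails the general Concomitant definition while meeting its second sub-category. The last three rows, which do not use the rule, classify cleanly, so the fault lies in the missing-end rule and not in the category definitions alone.

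Nothing else in the SAP repairs this. The partial-date rule does not address an imputed end that precedes a known start. The instruction in 2.3.4 to count a subject once per medication and timing category does not choose between two categories.

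**The case against.** Several limits are fair, and they stand.

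- **Scope.** The rule covers only records with no end date at all and no ongoing tick. A reader might infer that any medication lacking an end date becomes Prior. That is not so: drugs ticked as ongoing and partial end dates are handled separately.
- **Drugs started on treatment.** A reader might infer that these are simply moved to Prior. The text does not establish that, because they also meet the start-date wording of Concomitant. The result is an unresolved conflict. Only drugs with an earlier start, or no start date, fall cleanly into Prior.
- **Per protocol set.** It is tempting to say that the rule hides prohibited drugs from the PPS decision. No section says that the summary table feeds that decision. Exclusions are settled case by case in a signed pre-analysis review before unblinding (SAP 2.2 and 5.5), the individual listing exists, and a recorded on-treatment start date stays in the data. The PPS analysis is itself supplementary (SAP 2.4.6).
- **Primary result.** The full analysis set ANCOVA uses treatment, stratification and baseline (SAP 2.4.2). It does not use medication timing.
- **Adverse event rule.** SAP 5.1.2 leans towards on-treatment, but only for partial dates that match the month or year of the first dose. It says nothing about wholly missing dates, so it contrasts in direction and is not a direct counterpart.
- **Data cleaning.** Edit checks and queries are planned (Protocol 10.3) and must be finished before lock (Protocol 10.6). A record with neither an end date nor an ongoing tick is a natural query. However, the documents do not specify that check, and the SAP rule exists for whatever remains unresolved.

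It can also be said that treating every such record as on-treatment only moves the error the other way. That is partly right: preventing impossible dates needs only the narrower ban on an end before a known start. The ban alone would still leave drugs begun before randomisation assumed to have stopped, so the default direction also needs changing.

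**Conclusion.** The point holds as a minor defect in a stated rule. For a record with no end date and ongoing not ticked, SAP 5.1.3 yields either a Prior label that may be wrong (earlier or missing start) or an impossible end date with two competing categories (start on or after the first dose). The direct consequence is confined to the Prior/Concomitant/Post summary table, where on-treatment use can be understated.

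The size cannot be stated. The documents do not say how many records will lack an end date, and any count of changed PPS classifications would be a guess. A change in PPS membership is possible, because that decision weighs extent of treatment, but nothing makes it follow from the rule. The primary analysis is unaffected. The classification results follow from the SAP wording. The only added assumption is the day-56 last dose, which matters only to which start days count as during or after treatment.

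**What to change.** Replace the missing-end rule in SAP 5.1.3 with wording such as: where a medication has no end date and is not marked as ongoing, no end date earlier than a recorded start will be imputed; the medication will be classified as concomitant, or as post if it started after the last dose of randomised treatment, unless the available information shows that it stopped before the first dose.

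This removes the impossible dates and the double classification, and it resolves remaining uncertainty towards on-treatment exposure. It needs one sentence in the SAP and a small change to the derivation code. The cost is that a few drugs that had in fact stopped before randomisation may be counted as concomitant.

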## 5.1.3.1 Other imputations

NA

## 5.2 AEs coding/grading

All AEs and medical history verbatim terms were encoded as SOC and PT using MedDRA, latest version available when approving the data management plan (DMP). Severity is graded as mild, moderate and severe. Relation to treatment is captured as related and not related.

## 5.3 Laboratory parameters derivations

NA

## 5.4 Statistical models

NA

## 5.4.1 Analysis supporting primary objective(s)

See Section 2.4

## 5.4.2 Analysis supporting secondary objective(s)

See Section 2.5

# 5.5 Rule of exclusion criteria of analysis sets

The final criteria for PPS, regarding which protocol deviations and other criteria that warrant exclusions will be determined when all data on protocol deviations are available and before breaking the blind. Final classification of subjects according to study populations will be documented and included in a "pre-analysis review" document, which will be signed before unblinding.

# 5.6 Tables, Listings and Figures Overview

# Tables to be Produced for the Clinical Study Report (Section 14 according to ICH E3)

(Table numbers refer to section numbers in ICH E3.)

## 14.1 Demography and Background Characteristics

| Table                             | SAF | FAS | PPS |
|-----------------------------------|-----|-----|-----|
| Subject disposition               | X   |     |     |
| Subject disposition by strata     | X   |     |     |
| Subject discontinuation           | X   |     |     |
| Subject discontinuation by strata | X   |     |     |
| Demography                        | Х   |     |     |
| Demography by strata              | X   |     |     |
| Number of subjects by visit       | X   |     |     |
| Medical history                   | Х   |     |     |

# 14.2 EFFICACY DATA

# 14.2.1 Primary Endpoint

| Table  | SAF | FAS | PPS |
|--|-----|-----|-----|
| Summary of Myocardial energetic efficiency by visit and change from baseline   |     | Х   | Х   |
| Analysis of change from baseline in Myocardial energetic efficiency (ANCOVA)   |     | Х   | Х   |
| Boxplots of change from baseline in Myocardial energetic efficiency  |     | Х   | Х   |
| Summary of Myocardial energetic efficiency by visit and change from baseline by strata                                       |     | Х   | Х   |
| Analysis of change from baseline in Myocardial
energetic efficiency (ANCOVA) including treatment by
strata interaction |     | X   | Х   |
| Summary of Viable myocardium energetic efficiency by visit and change from baseline  |     | X   | X   |
| Analysis of change from baseline in Viable myocardium
energetic efficiency (ANCOVA)                                       |     | Х   | Х   |
| Boxplots of change from baseline in Viable Myocardial energetic efficiency   |     | Х   | Х   |

# 14.2.2 Secondary Endpoints

| Table  | SAF | FAS | PPS |
|--|-----|-----|-----|
| Summary of Ejection fraction (Echocardiography) by visit and change from baseline                              |     | Х   |     |
| Analysis of change from baseline in Ejection fraction
(Echocardiography) (ANCOVA)                           |     | Х   |     |
| Summary of N-terminal prohormone brain natriuretic peptide (NT-proBNP) by visit and change from baseline       |     | Х   |     |
| Analysis of change from baseline in N-terminal
prohormone brain natriuretic peptide (NT-proBNP)
(ANCOVA) |     | X   |     |
| Summary Systemic BP during PET by visit and change from baseline   |     | Х   |     |

| Analysis of change from baseline in Systemic BP
(ANCOVA) collected in relation to Echocardiograph
and PET                 | X |
|---|---|
| Summary of Systemic vascular resistance (SVR) by visit and change from baseline   | X |
| Analysis of change from baseline in Systemic vascular
resistance (SVR) (ANCOVA)  | X |
| Summary of Coronary Vascular Resistance by visit and change from baseline   | X |
| Analysis of change from baseline in Coronary Vascular
Resistance (ANCOVA)  | X |
| Summary of Cardiac Oxygen Consumption (k mono ) by visit and change from baseline                                    | X |
| Analysis of change from baseline in Cardiac Oxygen
Consumption (k mono ) (ANCOVA)                                 | X |
| Summary of Resting perfusion (PET) by visit and change from baseline  | X |
| Summary of Viable myocardiumResting perfusion
(PET) by visit and change from baseline  | X |
| Summary of Viable myocardium clearance rate (PET)
by visit and change from baseline  | X |
| Summary of Left ventricle mass (Echocardiography) by visit and change from baseline   | X |
| Summary of Stroke volume (Echocardiography) by visit and change from baseline   | X |
| Summary of Cardiac output (Echocardiography) by visit and change from baseline  | X |
| Summary of Left ventricular mechanical work (SBP x
SV x HR)/ LV mass (Echocardiography) by visit and
change from baseline | X |
| Summary of Global Longitudinal Strain
(Echocardiography) by visit and change from baseline                                   | X |
| Summary of left ventricular systolic volume
(Echocardiography) by visit and change from baseline                             | X |
| Summary of left ventricular diastolic volume
(Echocardiography) by visit and change from baseline                            | X |
|   |   |

## 14.3 SAFETY DATA

## 14.3.1 Display of Adverse Events

| Item   | SAF | FAS | PPS |
|--|-----|-----|-----|
| Summary of Treatment-Emergent Adverse Events   | Х   |     |     |
| Summary of Treatment-Emergent Adverse Events by strata                                     | Х   |     |     |
| Treatment-Emergent Adverse Events by System Organ
Class and Preferred Term              | Х   |     |     |
| Treatment-Emergent Adverse Events by Severity and
System Organ Class and Preferred Term | Х   |     |     |
| Treatment-Emergent Adverse Events by Relation and
System Organ Class and Preferred Term | Х   |     |     |

## 14.3.2 Listings of Deaths, Other Serious Adverse Events, and Other Significant Adverse Events

| Item                                 | SAF | FAS | PPS |
|--------------------------------------|-----|-----|-----|
| Listing of Serious Adverse Events    | Х   |     |     |
| Adverse Events Leading to Death      | Х   |     |     |
| Adverse Events Leading to Withdrawal | X   |     |     |

### 14.3.3 Reserved for narratives

## 14.3.4 Laboratory Assessments

| Item   | SAF | FAS | PPS |
|--|-----|-----|-----|
| Abnormal Laboratory Value Listing            | Х   |     |     |
| Summary of Safety Laboratory Assessments     | X   |     |     |
| Safety Laboratory Assessments Shift Table    | X   |     |     |
| Summary of Laboratory Biomarker Assessments  |     | Х   |     |
| Biomarker Laboratory Assessments Shift Table |     | Х   |     |

## 14.3.5 Extent of Exposure

| Item | SAF | FAS | PPS |
|------|-----|-----|-----|
|------|-----|-----|-----|

| Exposure to Study Drug                      | Х |  |
|---|---|--|
| Summary of subjects by dose group and visit | Х |  |
| Compliance                                  | Х |  |

# 14.3.6 Vital Signs

| Item                    | SAF | FAS | PPS |
|-------------------------|-----|-----|-----|
| Summary of Vital Signs  | Х   |     |     |
| Vital Signs Shift Table | Х   |     |     |

